3.1.3 ECOG Performance Status (PS) 0, 1, or 2 (Appendix A)

3.1.4 The following laboratory values obtained ≤ 21 days prior to registration and confirmed prior to the first dose of study drug:

- ANC $\geq 1000/\mu\text{L}$
- PLT $\geq 50,000/\mu\text{L}$. Platelet transfusions to help patients meet eligibility criteria are not allowed within 3 days before study enrollment.
- Total bilirubin ≤ 1.5 mg/dL (If total is elevated check direct and if normal patient is eligible.)
- AST $\leq 3 \times$ institutional upper limit of normal (ULN)
- ALT $\leq 3 \times$ institutional upper limit of normal (ULN)
- WBC $\geq 2000/\mu\text{L}$

3.1.5 Ability to understand and willingness to sign a written informed consent before performance of any study-related procedure not part of normal medical care, with the understanding that consent may be withdrawn by the subject at any time without prejudice to future medical care.

CONFIDENTIAL

This document is confidential. Do not disclose or use except as authorized.

3.1.6 Female patients who are postmenopausal for at least 1 year before the screening visit or are surgically sterile. Females of childbearing potential* must have a negative serum or urine pregnancy test with a sensitivity of at least 25 mIU/mL within 10 – 14 days and again within 24 hours prior to prescribing lenalidomide for Cycle 1 (prescriptions must be filled within 7 days as required by Revlimid REMS®) and must either commit to continued abstinence from heterosexual intercourse or begin TWO acceptable methods of birth control, one highly effective method and one additional effective method AT THE SAME TIME, at least 28 days before she starts taking lenalidomide. Females of reproductive potential must agree to follow instructions for method(s) of contraception for the duration of treatment with any study drug(s) plus 5 half-lives of study plus 30 days (duration of ovulatory cycle) for a total of 120 days after their last dose of lenalidomide (Revlimid). Women must not breastfeed.

Female patients who are of childbearing potential must use contraception for 5 half-lives plus 30 days after their last dose of nivolumab for a total of 5 months.

* *A female of childbearing potential is a sexually mature female who:*

- *Has not undergone a hysterectomy (the surgical removal of the uterus) or bilateral oophorectomy (the surgical removal of both ovaries) or*

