- *Has not been naturally postmenopausal (amenorrhea following cancer therapy does not rule out childbearing potential) for at least 24 consecutive months (i.e., has had menses at any time during the preceding 24 consecutive months)*

3.1.7 All study participants must be registered into the mandatory Revlimid REMS® program, and be willing and able to comply with the requirements of the REMS® program.

3.1.8 Females of reproductive potential must adhere to the scheduled pregnancy testing as required in the Revlimid REMS® program.

3.1.9 Men must agree to use a latex condom during sexual contact with a female of childbearing potential even if they have had a successful vasectomy during the entire study treatment period and through 154 days after the last dose of lenalidomide (Revlimid) or agree to practice true abstinence when this is in line with the preferred and usual lifestyle of the subject. (Periodic abstinence [eg, calendar, ovulation, symptothermal, post-ovulation methods] and withdrawal are not acceptable methods of contraception.)

Men who are sexually active with women who are of childbearing potential must adhere to contraception for a period of 5 half-lives plus 90 days for a

CONFIDENTIAL

This document is confidential. Do not disclose or use except as authorized.

total of 7 months after their last dose of nivolumab.

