5.4.4 Pregnancy

- Female patients participating in this study should avoid becoming pregnant, and male patients should avoid impregnating a female partner. Non-sterilized female patients of reproductive age group and male patients should use effective methods of contraception through defined periods during and after study treatment as specified below.

CONFIDENTIAL

This document is confidential. Do not disclose or use except as authorized.

- Female patients must meet 1 of the following:
 - Postmenopausal for at least 1 year before the screening visit
 - Surgically sterile
 - If they are of childbearing potential, agree to practice 2 effective methods of contraception from the time of signing of the informed consent form through 120 days after the last dose of lenalidomide (Revlimid) of study drug
 - Women who are of childbearing potential, agree to practice contraception for a period of 5 months after their last dose of nivolumab
 - Agree to practice true abstinence, when this is in line with the preferred and usual lifestyle of the subject.
 - Periodic abstinence (eg, calendar, ovulation, symptothermal, postovulation methods) and withdrawal are not acceptable methods of contraception.
- Male patients, even if surgically sterilized (ie, status postvasectomy) must agree to 1 of the following:
 - Practice effective barrier contraception during the entire study treatment period and through 154 days after the last dose of lenalidomide (Revlimid)
 - Men receiving nivolumab who are sexually active with women of childbearing potential must adhere to contraception for a period of 7 months after the last dose of nivolumab
 - Agree to practice true abstinence, when this is in line with the preferred and usual lifestyle of the subject.
 - Periodic abstinence (eg, calendar, ovulation, symptothermal, postovulation methods for the female partner) and withdrawal are not acceptable methods of contraception.

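### Section 5.4.4 and the opening of 3.1.6 use a 1-year menopause test, but the 3.1.6 footnote uses 24 months (minor patient-safety inconsistency)

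*Combined protocol and SAP*

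**What the plan says.** Section 5.4.4 (Pregnancy) introduces its list for women with "Female patients must meet 1 of the following". The first two entries are "Postmenopausal for at least 1 year before the screening visit" and "Surgically sterile". Contraception comes in separate, later entries: two methods through 120 days after lenalidomide, contraception for 5 months after nivolumab, or true abstinence. The lead-in above the list says: "Non-sterilized female patients of reproductive age group and male patients should use effective methods of contraception". The section does not define the reproductive age group and does not refer to 3.1.6.

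Section 3.1.6 opens with an incomplete sentence using the same tests: "Female patients who are postmenopausal for at least 1 year before the screening visit or are surgically sterile". It then sets pregnancy testing, and abstinence or two contraceptive methods, for females of childbearing potential. Its footnote describes such a female by two conditions. The one on surgery names only removal of the uterus or of both ovaries. The one on menopause, offered as the alternative, reads: "Has not been naturally postmenopausal (amenorrhea following cancer therapy does not rule out childbearing potential) for at least 24 consecutive months".

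**The concern.** Two rules in one protocol decide differently whether a woman needs contraception and pregnancy testing. Section 3.2.7 describes lenalidomide as potentially teratogenic or abortifacient. Sections 1.1 and 5.1 let participants stay on it after the September 2017 partial clinical hold. A site that works from 5.4.4, the section on managing clinical events, could conclude that a woman 15 months past her last period has met the requirement, although the footnote still counts her as of childbearing potential. The harm to be avoided is fetal exposure. It is unlikely in this population, but serious.

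**Working it through.** No design figure is involved, so the check is a comparison of the texts.

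**Inputs.** 5.4.4 and the first sentence of 3.1.6: 1 year (12 months) of menopause with no cause stated, or surgical sterility with no procedure stated. 3.1.6 footnote: hysterectomy or bilateral oophorectomy, or 24 consecutive months of natural menopause, with amenorrhea after cancer treatment not counted. Gap in the menopause threshold: 24 − 12 = 12 months.

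**How the footnote is read.** It joins two negative conditions with *or*. Taken literally, a woman stays of childbearing potential unless she has had both the surgery and the menopause. The sensible reading is that either one is enough, and that reading is used here. The mismatch exists under both; the literal one only widens it.

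**Classification, group by group.**

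| Woman | 5.4.4 list | 3.1.6 footnote | Result |
|---|---|---|---|
| Natural menopause, 12 to under 24 months | Meets the first entry | Of childbearing potential | Direct conflict |
| Amenorrhea for 1 year or more after cancer treatment | Depends on what postmenopausal covers | Of childbearing potential | Possible conflict |
| Sterilized by another operation, such as tubal ligation | Depends on what surgically sterile covers | Of childbearing potential | Possible conflict |
| Natural menopause, 24 months or more | Meets the first entry | Not of childbearing potential | Agree |
| Hysterectomy or bilateral oophorectomy | Meets the second entry | Not of childbearing potential | Agree |

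The second group can exist in this trial: 3.2.4 excludes another malignancy only within 2 years of enrollment, and 3.2.2 lets some previously treated patients enter after discussion with the PI. For the third group, the men's part of 5.4.4 uses *sterilized* for vasectomy, which removes no organ, so a site could read the women's entry as broadly.

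**Illustrative dates.** Assume a last start on 30 September 2017, 12 cycles of 28 days, lenalidomide on days 1 to 21, and no delays.

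- Last lenalidomide dose: 11 × 28 + 21 = treatment day 329, which is 24 August 2018.
- Plus 120 days: 22 December 2018, 333 days after the protocol version of 23 January 2018.
- A woman at exactly 12 months on 30 September 2017 reaches 24 months on 30 September 2018, 250 days after that version.
- If nivolumab was last given on 30 September 2017, its 5 months end on 28 February 2018, 36 days after that version.

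These dates show only that the question was still live when the current version was issued. They are not bounds. The documents say only September 2017 for the hold, Section 6.1 allows delays of 3 weeks (longer with approval), and Section 2.9.2 allows up to 3 weeks after stem cell collection.

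**The case against.** The strongest reply is that 3.1.6 already settles the matter. Its testing and contraception duties attach to women of childbearing potential, a phrase defined only in its footnote. They are not confined to entry: they cover the whole of treatment plus 120 days after lenalidomide and 5 months after nivolumab. Sections 3.1.7, 3.1.8 and 8.2.8 make REMS compliance mandatory, and footnote 12 of the study calendar (Section 10) repeats the REMS duty. Much of this stands and is why the point is minor. It does not remove the conflict. Section 5.4.4 sends no one to 3.1.6, and a reader who goes there meets the 1-year wording first, so the conflict also sits inside 3.1.6. The documents give no REMS menopause threshold, and calendar footnote 12 applies to women of childbearing potential, so that safeguard depends on the same classification.

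A second reply is that the 5.4.4 list is not a clean any-one list. The nivolumab entry adds to the lenalidomide entry, and the line rejecting periodic abstinence is nothing a patient could meet. So the absence of a contraception duty for the first two entries is inferred from the lead-in to the list; 5.4.4 does not state it. That is fair. The inference is direct, but the loose list is itself a defect: taken at its word, a woman of childbearing potential could satisfy it through the nivolumab entry alone.

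A reader might also infer that all three groups above are in open contradiction. The documents do not support that. Section 5.4.4 says postmenopausal, not amenorrheic, and never says that surgical sterility is wider than the footnote's two operations. Those two groups are ambiguities.

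**Conclusion.** The inconsistency is real and minor. One group, women 12 to under 24 months past natural menopause, is classified differently by 5.4.4 and the 3.1.6 footnote. Two more may be, because 5.4.4 does not define its terms. The documents do not say how many women are affected, and it may be none. Accrual has closed, so no new participant is exposed. Sample size, decision rule, endpoints and analyses are untouched.

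A reader might infer that the protocol allows these women to take lenalidomide unprotected, or that the mismatch lasts a fixed number of days. Neither follows. The contraception duty in 3.1.6 continues through the relevant periods for anyone its footnote covers, and the day counts rest on an assumed start date and no delays.

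The conclusion assumes that meeting one entry in 5.4.4 is enough and that either arm of the footnote removes childbearing potential.

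**What to change.** 1. In 5.4.4, replace the first two entries with one positive statement: *Not of childbearing potential: uterus or both ovaries surgically removed, or natural menopause lasting 24 consecutive months or more; amenorrhea after cancer treatment does not qualify.* A bare cross-reference would bring in the footnote's double negative.
2. For women of childbearing potential who do not practice true abstinence, require the lenalidomide two-method entry and the nivolumab entry together, so that neither alone satisfies the list.
3. Delete the opening 1-year sentence of 3.1.6, or align it with the footnote.
4. Re-check the classification of women still taking lenalidomide, within 120 days of their last lenalidomide dose, or within 5 months of their last nivolumab dose.

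The cost is wording in two sections and one check of current participants. The downside is pregnancy testing and contraception for at most a few women, possibly none.

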5.5 Criteria for Taking a Participant Off Protocol Therapy

Patients will be informed that they have the right to withdraw from the study at any time for any reason, without prejudice to their medical care.

In the absence of treatment delays due to adverse event(s), treatment may continue for 12 cycles or until one of the following criteria applies:

- Progression to overt Multiple Myeloma
- Intercurrent illness that prevents further administration of treatment

CONFIDENTIAL

This document is confidential. Do not disclose or use except as authorized.

- Unacceptable adverse event(s)
- Participant demonstrates an inability or unwillingness to comply with the oral medication regimen and/or documentation requirements
- Participant decides to withdraw from the protocol therapy
- General or specific changes in the participant's condition render the participant unacceptable for further treatment in the judgment of the treating investigator

Participants will be removed from the protocol therapy when any of these criteria apply. The reason for removal from protocol therapy, and the date the participant was removed, must be documented in the case report form (CRF). Alternative care options will be discussed with the participant.

A Treatment Ended/Off Study Form will be filled out when a participant is removed from protocol therapy. This form will be provided by the lead site. External sites should submit the form to the Research Project Manager.

In the event of unusual or life-threatening complications, treating investigators must immediately notify the Overall PI, [name] at [contact].

5.6 Duration of Follow Up

Participants will be followed for **3 years** after removal from protocol therapy or until progression to active symptomatic MM or need for new therapy, whichever occurs first. Participants removed from protocol therapy for unacceptable adverse event(s) will be followed until resolution or stabilization of the adverse event.

5.7 Criteria for Taking a Participant Off Study

Participants will be removed from study when any of the following criteria apply:

- Lost to follow-up
- Withdrawal of consent for data submission
- Death
- Progression to active myeloma and subsequent treatment

The reason for taking a participant off study, and the date the participant was removed, must be documented in the case report form (CRF).

CONFIDENTIAL

This document is confidential. Do not disclose or use except as authorized.

A Treatment Ended/Off Study Form will be filled out when a participant is removed from protocol therapy. This form will be provided by the lead site. External sites should submit the form to the Research Project Manager.

6. DOSING DELAYS/DOSE MODIFICATIONS

6.1 Recommended Criteria for Beginning or Delaying a Subsequent Treatment Cycle

Patients must meet eligibility criteria on Cycle 1 Day 1 to begin treatment. There are no pre-treatment criteria to begin a new cycle of nivolumab.

For a new cycle of treatment with lenalidomide to begin, the patient must meet the following criteria:

- ANC must be $\geq 1,000/\mu\text{L}$.
- Platelet count must be $\geq 50,000/\mu\text{L}$.
- All other clinically significant, study drug related non hematologic toxicity must have resolved to \leq Grade 1 or to baseline condition

If the participant fails to meet the above-cited criteria for initiation of a new cycle of treatment on day 1 of the cycle, dosing of all medications should be delayed for 1 week. At the end of that time, the participant should be re-evaluated to determine whether the above criteria have been met. If the participant continues to fail to meet the above-cited criteria, delay therapy and continue to re-evaluate. The maximum delay for toxicity related to study treatment before treatment is permanently discontinued will be 3 weeks. If a delay of > 3 weeks is clinically necessary, and the patient is showing benefit from treatment, the patient may continue on study after discussion and approval by the Principal Investigator.

If any one of the study medications is permanently discontinued for any reason including toxicity, or FDA mandate, the patient may remain on the study at the discretion of the principal investigator.

6.2 Nivolumab

No dose reductions for Nivolumab are allowed. If Nivolumab is held on Day 1 of a new cycle, treatment with Lenalidomide/Dexamethasone will also be delayed. If Nivolumab is held during any cycle on day 15, the treating investigator should decide if lenalidomide and/or dexamethasone will be skipped using recommended guidance for retreatment below. Nivolumab may be delayed for up to 21 days or 3 weeks. A delay of up to 14 days will be allowed for participants for non-AE related events (i.e.; vacation, family emergency, etc) after discussion with the overall PI. If an alternate treatment plan for a suspected nivolumab related toxicity is proposed and is not listed in Table 11, you must first discuss and obtain approval from the Overall PI.

Dose delays and modifications will be made as indicated in the following table(s). The

CONFIDENTIAL

This document is confidential. Do not disclose or use except as authorized.

descriptions and grading scales found in the revised NCI Common Terminology Criteria for Adverse Events (CTCAE) version 4.03 will be utilized for dose delays and dose modifications. A copy of the CTCAE version 4.03 can be downloaded from the CTEP website

http://ctep.cancer.gov/protocolDevelopment/electronic_applications/ctc.htm.

* If any one of the study medications is permanently discontinued for any reason including toxicity, or FDA mandate, the patient may remain on the study at the discretion of the principal investigator.

Table 11 Suggested Guidelines for Nivolumab Suspected Toxicity

CTCAE 4.0 Category	CTCAE Grade	Nivolumab Action
Pneumonitis (See Section 6.2.1 for management guidelines)	Grade 1	Continue to treat- Do NOT OMIT
	Grade 2	Hold dose until resolved to \leq Grade 1
	\geq Grade 3	Permanently discontinue nivolumab
Colitis (See Section 6.2.2 for management guidelines)	Grade 1	Continue to treat- Do NOT OMIT
	Grade 2 or Grade 3	Hold dose until resolved to \leq Grade 1
	Grade 4	Permanently discontinue nivolumab
Increase in AST and/or ALT (See Section 6.2.3 for management guidelines)	Grade 1	Continue to treat- Do NOT OMIT
	Grade 2	Hold dose until resolved to \leq Grade 1
	\geq Grade 3	Permanently discontinue nivolumab
Increase in Blood Bilirubin (See Section 6.2.3 for management guidelines)	Grade 1	Continue to treat- Do NOT OMIT
	Grade 2	Hold dose until resolved to \leq Grade 1
	\geq Grade 3	Permanently discontinue nivolumab
Increase in Creatinine (See Section 6.2.4 for management guidelines)	Grade 1	Continue to treat- Do NOT OMIT
	Grade 2 or Grade 3	Hold dose until resolved to \leq Grade 1
	Grade 4	Permanently discontinue nivolumab
All other related toxicities not listed previously in this table (See Section 6.2.6 for management guidelines)	Grade 1	Continue to treat- Do NOT OMIT
	Grade 2	Continue to treat- Do NOT OMIT
	Grade 3	Hold dose until resolved to \leq Grade 1
	Recurrent Grade 3 or	Permanently discontinue nivolumab

CONFIDENTIAL

This document is confidential. Do not disclose or use except as authorized.

	Grade 4	
--	---------	--

If the patient discontinues nivolumab, he or she does not need to come off protocol therapy

6.2.1 Immune-Mediated Pneumonitis

Monitor patients for signs and symptoms of pneumonitis. Administer corticosteroids at a dose of 1 to 2 mg/kg/day prednisone equivalents for Grade 2 or greater pneumonitis, followed by corticosteroid taper. Permanently discontinue nivolumab for severe (Grade 3) or life-threatening (Grade 4) pneumonitis and withhold nivolumab until resolution for moderate (Grade 2) pneumonitis.

6.2.2 Immune-mediated colitis

Monitor patients for immune-mediated colitis. Administer corticosteroids at a dose of 1 to 2 mg/kg/day prednisone equivalents followed by corticosteroid taper for severe (Grade 3) or life-threatening (Grade 4) colitis. Administer corticosteroids at a dose of 0.5 to 1 mg/kg/day prednisone equivalents followed by corticosteroid taper for moderate (Grade 2) colitis of more than 5 days duration; if worsening or no improvement occurs despite initiation of corticosteroids, increase dose to 1 to 2 mg/kg/day prednisone equivalents. Withhold NIVOLUMAB for Grade 2 or 3 immune-mediated colitis. Permanently discontinue NIVOLUMAB for Grade 4 colitis or for recurrent colitis upon restarting NIVOLUMAB

6.2.3 Immune-Mediated Hepatitis

Monitor patients for abnormal liver tests prior to and periodically during treatment. Administer corticosteroids at a dose of 1 to 2 mg/kg/day prednisone equivalents for Grade 2 or greater transaminase elevations, with or without concomitant elevation in total bilirubin. Withhold nivolumab for moderate (Grade 2) and permanently discontinue nivolumab for severe (Grade 3) or life-threatening (Grade 4) immune-mediated hepatitis.

6.2.4 Immune-Mediated Nephritis and Renal Dysfunction

Monitor patients for elevated serum creatinine prior to and periodically during treatment. Administer corticosteroids at a dose of 1 to 2 mg/kg/day prednisone equivalents followed by corticosteroid taper for life-threatening (Grade 4) serum creatinine elevation and permanently discontinue nivolumab. For severe (Grade 3) or moderate (Grade 2) serum creatinine elevation, withhold nivolumab and administer corticosteroids at a dose of 0.5 to 1 mg/kg/day prednisone equivalents followed by corticosteroid taper; if worsening or no improvement occurs, increase dose of corticosteroids to 1 to 2 mg/kg/day prednisone equivalents and permanently discontinue nivolumab.

6.2.5 Immune-Mediated Hypothyroidism and Hyperthyroidism

Monitor thyroid function prior to and periodically during treatment. Administer hormone replacement therapy for hypothyroidism. Initiate medical management for control of

CONFIDENTIAL

This document is confidential. Do not disclose or use except as authorized.

hyperthyroidism. There are no recommended dose adjustments of nivolumab for hypothyroidism or hyperthyroidism.

